14.4 Procedures for Reporting any Deviation(s) from the Original Statistical Analysis Plan

Minor alterations can be made by agreement with the CI and documented accordingly.

14.5 Interim analysis and criteria for early study termination

As this is a feasibility study assessing the ease and safety of application of the glue, there will be no planned interim analysis. Due to the small number of patients needed for the study, and the acceptable leak rate of 20%, it is entirely possible that consecutive participants suffer an anastomotic leak through chance alone. Each anastomotic leak will be reviewed as a serious adverse event. If there are any concerns that a leak has been caused by the BioGlue applied (for example, the anastomosis has become abnormally adherent to structures in the chest at re-operation) then a serious adverse device effect has occurred, and the study paused while this is reviewed. If there are 5 consecutive anastomotic leaks in a row, this will trigger an internal review and an independent data monitoring committee formed and convened to review the study. If there are more SAEs than expected, raised by the research team inputting data, this will be highlighted to the PI. Early termination of the study can then be considered by the PI.

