	 2. planned for elective minimally invasive oesophagectomy at Queen Alexandra Hospital 3. Able to provide informed consent Exclusion criteria: Provious adverse reaction to PieClue or one of ite 				
	constituent ingredients.				
Planned Sample Size	30				
Follow-up duration	6 weeks post-surgery				
Planned Study Period	1 year				
Primary Objective	To assess whether it is technically feasible to use BioGlue at the anastomosis for oesophagectomy				
Secondary Objectives	To describe adverse events up to 6 weeks post-surgery.				
Objectives	To describe surgical process indicators and surgical outcomes.				
Primary Endpoint	Technical feasibility of applying the BioGlue				
Secondary Endpoints	Post-operative complications up to six weeks, graded with the Clavien- Dindo scale Anastomotic leak rate All-cause mortality up to 6 weeks follow up Operative duration Time to discharge from hospital Unplanned return to ITU Unplanned return to theatre Unplanned return to surgical high care unit Acceptability of the product to the surgeons and the theatre team (assessed using qualitative methods) Number of CT scans Use of antibiotics (duration, indication and type)				
Intervention (s)	Application of adhesive BioGlue in addition to standard anastomotic formation in patients undergoing minimally invasive oesophagectomy.				

3.	ABBREVIATIONS
AE	Adverse event
BSA	Bovine serum albumin
CPET	Cardiopulmonary exercise testing
СТ	Computed tomography
ITU	Intensive treatment unit
MDT	Multi-disciplinary team
MIO	Minimally invasive oesophagectomy
NHS	National Health Service
PPI	Public patient involvement
PRA	Patient research ambassador
QAH	Queen Alexandra Hospital, Portsmouth Hospitals NHS Trust
RCT	Randomised controlled trial
SAE	Serious adverse event
TMG	Trial management group
TOG	Trials oversight group

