12. ASSESSMENT OF SAFETY (IF APPLICABLE)

12.1 Definitions

Adverse Event:

Any untoward medical occurrence, unintended disease or injury, or any untoward clinical signs (including an abnormal laboratory finding) in participants, users or other persons concerned with the medical device. These may, or may not be, considered related to the investigational material (i.e. BioGlue), related procedure or comparator. If the AE is considered to have a reasonable causal relationship with the material, then it is considered to be an Adverse Device Effect (ADE).

To fully address the potential adverse events following oesophagectomy we must include the established complications from surgery. Participants would be at risk of these complications irrespective of whether they receive the intervention or not. They will all be considered an expected adverse event and include (2):

- Pneumonia.
- Atrial dysrhythmia.
- Anastomotic leak.
- Gastric conduit necrosis.
- Chyle leaks.
- Recurrent laryngeal nerve injury.

BioGlue's manufactures CryoLife, detail the potential local and systemic adverse effects of the device in their product literature. These complications are specific to the adjunctive use of BioGlue during soft tissue repair, and include:

- Failure of product to adhere to intended tissue.
- Application of adhesive to unintended tissue.

- Inflammatory and immune response.
- Allergic reaction.
- Mineralization of tissue.
- Local tissue necrosis.
- Damage to normal vessels or tissue.
- Blood vessel, bronchial or luminal obstruction.
- Thrombosis, thromboembolism and pulmonary embolism.

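### Section 14.5 requires a study pause only for a leak suspected to be caused by BioGlue, although section 12.1 defines device effects more widely and lists harms that need not involve a leak

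*Protocol*

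**What the plan says.** Protocol section 14.5 plans no interim analysis and sets three safety routes.

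- **Suspected device-caused leak.** "If there are any concerns that a leak has been caused by the BioGlue applied", "then a serious adverse device effect has occurred, and the study paused while this is reviewed". The example given is abnormal adherence of the anastomosis to chest structures, found at re-operation.
- **Run of leaks.** "If there are 5 consecutive anastomotic leaks in a row, this will trigger an internal review", and an independent data monitoring committee is then to be formed. No pause is stated.
- **Serious events in general.** "If there are more SAEs than expected, raised by the research team inputting data, this will be highlighted to the PI". After that, "Early termination of the study can then be considered by the PI". No number, comparator or pause is given.

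Section 12.1 is broader. An adverse event becomes an adverse device effect "If the AE is considered to have a reasonable causal relationship with the material", and later in the section also when it results from deployment, instructions for use or malfunction. Its list of product-specific effects includes "Blood vessel, bronchial or luminal obstruction", together with local tissue necrosis, thromboembolic events and allergic reaction.

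Section 12.2 asks for REC reports of related and unexpected serious events within 15 days. Section 12.3 requires every adverse event to be recorded with severity, causality and expectedness, followed to resolution, and reported under the sponsor's SOP.

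**The concern.** The pause rule covers a narrower set of events than the protocol's own definition of a device effect. A serious event attributed to BioGlue that does not present as a leak meets the section 12.1 definition, yet section 14.5 attaches no pause to it.

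This matters because safety is part of the stated aim (section 6) and section 4 reports no documented use of the product at this anastomosis. Section 12.1 says the manufacturer cites no evidence on the alimentary tract. It also says that the review of adhesives at this anastomosis covered studies measuring only collagen synthesis, bursting pressure and leak. The protocol does cite other alimentary studies of BioGlue without such complications, but it acknowledges that the evidence is of poor quality. In that setting, one serious event judged to be caused by the device is informative, and the plan allows the next patient to be treated before it has been reviewed.

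**Working it through.** The protocol states no figure on this point, so the check is mainly a comparison of the text.

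**Step 1. What each route requires after a serious, non-leak event attributed to BioGlue**

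| Provision | Applies? | Pause required? | Review required before the next patient? |
|---|---|---|---|
| 14.5, suspected device-caused leak | No, unless it presents with a leak | – | – |
| 14.5, five consecutive leaks | No | – | – |
| 14.5, serious events above expectation | Only if the unquantified count is judged high | No | No; the PI may consider termination |
| 12.2, REC report | If related and unexpected | No | No; up to 15 days to report |
| 12.3, recording and sponsor SOP | Yes | None stated | None stated; SOP cited for reporting, content not shown |

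No row gives a required pause or a required prior review.

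**Step 2. Does the REC route reliably apply?** Section 12.2 defines unexpected as a type of event that the protocol does not list as expected. Section 12.1 expressly calls only the surgical complications expected. The product-specific list carries no such label, although it is a list of known potential effects. On one reading its events are reportable; on the other they are not. The text does not settle this.

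**Step 3. Exposure during the reporting window**

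Inputs: 30 patients (section 7.1), recruitment within 12 months and about 70 operations a year (section 9), 15 days (section 12.2).

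- At the planned recruitment rate: 30 × 15/365 = 1.2 patients.
- If every operation at the centre were included: 70 × 15/365 = 2.9 patients.

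So about one to three further patients could be treated within the reporting window alone.

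**Step 4. Illustrative chance that the gap is met**

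The rates p are assumptions. With independent patients, P(at least one event in 30) = 1 − (1 − p)^30.

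- p = 1%: 1 − 0.99^30 = 1 − 0.740 = 0.26
- p = 3%: 1 − 0.97^30 = 1 − 0.401 = 0.60
- p = 5%: 1 − 0.95^30 = 1 − 0.215 = 0.79

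**The case against.** The strongest reply is that section 14.5 discusses leaks because leak is the event most in view. Its sentence links the classification as a serious adverse device effect directly to the pause, so it could be read as pausing for any such effect, with the leak as the worked case. Nothing forbids a pause for other events, and the investigators could pause voluntarily. This stands to the extent that the text does not exclude a pause. It does not supply a requirement, because the condition in the sentence is a concern about a leak.

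Several stronger readings are tempting but not supported.

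- **A reader might infer that a non-leak device effect merely adds to a count of serious events.** Sections 12.2 and 12.3 require individual recording, a causality assessment, SOP handling and possibly an REC report. These are real safeguards, but they are recording and reporting duties.
- **A reader might infer that the rule covers just one of the listed device harms.** Leak is on the surgical-complication list, not the product list. A product effect that presents as a leak, such as necrosis at the anastomosis, would meet the trigger.
- **A reader might infer that the PI alone decides.** Section 14.5 names the PI and nobody else for considering termination, but does not say alone. The SOP, which is not shown, may involve the sponsor.
- **A reader might infer that a standing body could take over at no cost.** "Trials oversight group" appears only in the abbreviations (section 3), with no membership or remit, and the data monitoring committee is to be formed only after five consecutive leaks.

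It is also fair to object that section 12.1 regards these reactions as so rare that harm is unlikely in a small group. The percentages above show only that rare events can occur in 30 patients. They do not measure how likely they are here.

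**Conclusion.** The concern holds in a limited form. Read as written, section 14.5 requires a pause only for a leak suspected to be caused by BioGlue. For any other serious adverse device effect under section 12.1, the protocol requires recording and reporting but no pause and no review before further patients are treated. This is a stated safety rule drawn more narrowly than the protocol's own definition, not a detail that could be left to a statistical analysis plan.

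The conclusion rests on the text and on the assumption that the unseen SOP does what the protocol cites it for, namely reporting. If the SOP already imposes a pause, the point reduces to saying so in section 14.5. The 26%, 60% and 79% depend entirely on assumed rates of 1%, 3% and 5% and carry no weight in the conclusion. The change should be made because it is cheap and bears on participant safety; no analysis result is affected.

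**What to change.** Reconcile section 14.5 with section 12.1 so that the existing pause-and-review provision applies to any serious adverse device effect, leak or not, including a death assessed as device-related. State who carries out the review and who decides on restart, preferably not the PI alone. If the trials oversight group is intended for this, give its membership and role, since at present it is only an abbreviation.

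In the same edit, say in section 12.1 or 12.2 whether the product-specific effects count as expected for REC reporting.

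The cost is a protocol wording change, an occasional short pause for an event that review then clears, and the time of whoever is named as reviewer. The protocol shows no standing body that already does this, so that time should not be assumed to be free.

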4. BACKGROUND AND RATIONALE

1. Oesophagectomy is the surgical treatment of oesophageal malignancy

The incidence of adenocarcinoma of the oesophagus has been observed to be rapidly increasing in the UK and the western world although incidence of squamous cell carcinoma of the oesophagus has been steadily declining. Cancer of the oesophagus (all types) is the sixth most common cancer in men and the ninth most common cancer in women worldwide with an observed six-fold increased incidence in men (8). The management of carcinoma of the oesophagus remains challenging (9). If a patient presents with malignancy which can be treated with curative intent, the surgical option is oesophagectomy. This was traditionally performed as an open operation but has progressed over the last 25 years and is now quite widely offered as a minimally invasive procedure – with laparoscopic and thoracoscopic stages (10). Within QA all oesophagectomies are undertaken with the aim of completion using minimally invasive techniques.

2. Anastomotic leaks are a major cause of perioperative morbidity and have a significant financial impact

One of the major risks of oesophagectomy is of a leak from the gastro-oesophageal anastomosis. Leak rates from the gastro-oesophageal anastomosis are quoted by NICE as 20%, which correlates with similar international figures e.g. The Dutch National database (1) (11). An anastomotic leak leads to prolonged in-hospital stay, can require an unplanned return to theatre, return to ITU and is associated with mortality as well as morbidity (2). Increases in mortality ranging from 18.2-35% have been quoted in the literature (12). As well as the distress, pain and other negative outcomes for the patients, the need for re-operation, return to ITU and increased length of stay come at significant financial cost. A Dutch team showed that a minor complication increases the cost of surgery for oesophageal cancer from an average of €59,167. Specifically, they showed the average cost of a patient who had suffered an anastomotic leak to be €44,268 (€20,792 higher than when the patient suffer no complications) (13).

3. BioGlue is already used, licensed and has been shown to be safe

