7. STUDY DESIGN

7.1 Summary of Study Design

This is a feasibility study to investigate the use of BioGlue (a mix of purified bovine serum albumin (BSA) and glutaraldehyde) to reinforce the anastomosis created during a minimally invasive oesophaegectomy. The study will be undertaken at a single centre and consecutive patients will be included up to a total of 30. Patients will receive the standard follow up following oesophagectomy, with a telephone consultation one week after discharge and then clinic appointments at two- and six-weeks. For the purposes of the study, all participants will also be reviewed by the study team six-weeks after the day of surgery. Patients will then continue to be followed up as normal, but outside of the bounds of this study.

The results from this study can guide the researchers in the further use of this product in the wider context of a randomised controlled trial.

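### The only numeric safety trigger, five anastomotic leaks in a row, has little sensitivity to a raised leak rate in 30 patients; a cumulative-count trigger for independent review should be added

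*Protocol*

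**What the plan says.** Protocol section 7.1 describes a single-centre study in which "consecutive patients will be included up to a total of 30". Section 14.5 states that "there will be no planned interim analysis" and takes as its benchmark "the acceptable leak rate of 20"%. The source of that figure is section 4: "Leak rates from the gastro-oesophageal anastomosis are quoted by NICE as 20"%, which the protocol says agrees with international data.

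Section 14.5 then sets out four safety steps:

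- Case review: "Each anastomotic leak will be reviewed as a serious adverse event".
- Pause: "If there are any concerns that a leak has been caused by the BioGlue applied", the event counts as a serious adverse device effect and the study is paused for review. Abnormal adherence seen at re-operation is the example given.
- Run rule: "If there are 5 consecutive anastomotic leaks in a row, this will trigger an internal review and an independent data monitoring committee formed", and that committee is convened to review the study.
- Excess events: "If there are more SAEs than expected, raised by the research team inputting data, this will be highlighted to the PI", after which the PI can consider early termination.

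Only the run rule contains a number, and only the run rule leads to an independent body. The protocol gives no probability that it will fire and sets no cumulative leak limit anywhere.

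**The concern.** The run rule discards most of the information in the leak record. It resets to zero after any patient without a leak and takes no account of how many leaks have accumulated. The protocol's reasoning, that consecutive leaks can happen by chance at 20%, is a good argument against reacting to short runs. It does not justify ignoring the total.

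A moderately raised leak rate is the kind of signal that case-by-case review is least able to see, because each leak may look like an ordinary surgical complication. Section 12.1 lists anastomotic leak among the expected events. Section 12.2 requires a report to the REC only when a serious event is both related and unexpected, so a leak would not meet that definition either. The protocol says there is no documented use of the product in oesophagogastric anastomoses (synopsis and section 4), and section 6 makes safety part of the case for a later randomised trial. An insensitive trigger could let an excess of leaks build up without anyone independent looking at it.

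**Working it through.** **Inputs from the protocol.** n = 30 (section 7.1); reference leak rate 20% (section 14.5); run length 5 (section 14.5); no planned interim analysis (section 14.5).

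**Assumptions.** Leaks are independent with constant probability p, and each is known in order of surgery. True rates of 30%, 40% and 50% are scenarios chosen for this check and do not come from the protocol.

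**Step 1: the protocol's own remark.** The protocol states no operating characteristic, so there is no figure to reproduce. Its remark about chance can be checked. At p = 0.20 the probability of at least one run of two or more leaks in 30 patients is 63.9%, so the remark is right for short runs.

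**Step 2: probability that the run rule fires.** Let a(n) be the probability of at least one run of five leaks within n patients. Then a(n) = 0 for n < 5, a(5) = p^5, and for n ≥ 6

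a(n) = a(n−1) + [1 − a(n−6)] × (1 − p) × p^5.

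- At p = 0.20: p^5 = 0.00032 and (1 − p)p^5 = 0.000256. An upper bound is 0.00032 + 25 × 0.000256 = 0.00672; the exact value is a(30) = 0.0067.
- At p = 0.40: p^5 = 0.01024 and (1 − p)p^5 = 0.006144. The upper bound is 0.01024 + 25 × 0.006144 = 0.164; the exact value is a(30) = 0.1556.

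| True leak rate | Leaks expected in 30 | Run rule fires | Does not fire |
|---|---|---|---|
| 20% | 6 | 0.7% | 99.3% |
| 30% | 9 | 4.4% | 95.6% |
| 40% | 12 | 15.6% | 84.4% |
| 50% | 15 | 36.8% | 63.2% |
| 60% | 18 | 64.4% | 35.6% |

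Simulation of 200,000 trials agrees (0.67%, 15.6% and 36.8% at 20%, 40% and 50%). The true rate must reach about 55% before the rule has an even chance of firing.

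**Step 3: what the rule can miss.** Four leaks followed by one patient without a leak, repeated six times, gives 4 × 6 = 24 leaks in 30 patients and never fires the rule. That is the extreme case. Given exactly 12 leaks in 30, the rule fires in 10.5% of the possible orderings.

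**Step 4: what a cumulative count could do with the same data.** As an illustration, look after every fifth patient and take the smallest count x with P(X ≥ x | n, 0.20) ≤ 0.05:

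| Patients | Count for review | P(X ≥ count) at 20% |
|---|---|---|
| 5 | 4 | 0.007 |
| 10 | 5 | 0.033 |
| 15 | 7 | 0.018 |
| 20 | 8 | 0.032 |
| 25 | 9 | 0.047 |

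Carrying the count forward exactly through all five looks, the probability that at least one look triggers is 7.4% at 20%, 38% at 30%, 76% at 40% and 95% at 50%. At 40% the cumulative probability is 37% by patient 10, 47% by patient 15, 63% by patient 20 and 76% by patient 25. Patients 26 to 30 have no further look. These figures are for the count trigger alone.

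**The case against.** The strongest reply is that the run rule is only a backstop. The plan relies first on review of every leak and on a pause that one suspicious leak can bring about. In that respect the pause is stricter than any count rule. At a true rate of 40%, about 12 leaks would each be reviewed. This is also a 30-patient feasibility study with a qualitative primary endpoint and leak rate as a descriptive secondary endpoint, so no planned result is invalidated by a weak trigger. The choice between a run rule and a count is partly a matter of design judgement.

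Much of this stands, and it limits the point to a should-fix. It does not remove it. None of the other steps is stated to be independent, none uses a cumulative count, and the pause depends on attributing an individual leak to the glue. An excess of ordinary-looking leaks could pass through all of them.

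Stronger readings are tempting but not supported:

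- A reader might infer that a high leak rate would certainly go unreviewed by a committee. The figures support usually, not always: the rule fires in about one trial in six at 40%.
- A reader might infer that the plan depends on an independent committee for its safety monitoring. Section 14.5 has no standing committee; one is formed only if the run occurs.
- A reader might take this as the hospital's first use of the product. Sections 4 and 5 report earlier uneventful bariatric use; the protocol says only that use in this anastomosis is undocumented.
- A reader might treat damage to the anastomosis as the main risk. Section 12.1 lists device risks without ranking them.
- A reader might call 20% the wrong reference. Its source is given openly and the centre's own rate is not in the document, so whether the two differ is unknown.

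**Conclusion.** The point holds as a limited one. The only numeric trigger, and the only stated route to independent review, is insensitive to a raised leak rate: it fires in 4.4% of trials at 30%, 15.6% at 40% and 36.8% at 50%. At double the acceptable rate, about 84% of trials would finish without the committee being formed.

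These figures rest on independent leaks at a constant rate in 30 treated patients. Clustering, for example by surgeon or during the learning phase, would make runs more likely. Fewer treated patients would lower every firing probability, and late recognition of a leak would delay the trigger. The 40% rate is an assumed scenario, but below an even chance of firing the conclusion is the same across 30% to 50%.

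Severity: should-fix, as a cheap improvement to patient protection. It does not show that the planned analyses are wrong.

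**What to change.** In section 14.5, keep the run rule and the existing case review and pause, and add a cumulative-count trigger for independent review. It should prompt review only, with no automatic stopping. It should be checked at regular intervals, be derived from the exact binomial against the stated 20%, and come with its probabilities of firing at 20%, 30%, 40% and 50%.

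The counts worked above (4 of 5, 5 of 10, 7 of 15, 8 of 20, 9 of 25) are an illustration and not a recommended rule. The investigators and the statistician should agree the final thresholds, and should decide whether the last five patients need a further look.

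The cost is one paragraph and a running tally of an event that is already recorded. Section 10.4 says almost all leaks occur before discharge, so the tally would be reasonably current. The statistical price is about a 7% chance of an unneeded review if the true rate is 20%.

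Optionally, the investigators could check the 20% reference against the centre's own audited leak rate.

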9. SAMPLING

All patients who are referred to the QAH and are found to have a diagnosis of oesophageal cancer which is deemed amenable to surgery following MDT discussion will be given the opportunity to take part in the trial.

Currently, around 70 oesophagectomies are performed at our centre annually. Recruitment is estimated to be completed within 12 months.

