10.5 Discontinuation/Withdrawal of Participants from Study Treatment

Patients withdrawing consent from the study will continue to have data which has already been collected used in the post-operative analysis. Once the surgery has occurred, there is no option for the removal of BioGlue and patients will be managed in the standard way.

Any patient who does not undergo surgery will not be included in the trial. Where surgery is abandoned intraoperatively for a surgical or anaesthetic reason, prior to the formation of the anastomosis, the patient will be withdrawn from the trial. This situation will be exceptionally uncommon.

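### Five consecutive leaks, the only numeric leak trigger in section 14.5, trigger a review but no stated pause, so more patients may receive BioGlue meanwhile

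*Protocol*

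**What the plan says.** Protocol section 14.5 plans no interim analysis and relies on event-driven rules instead.

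- **Every leak:** "Each anastomotic leak will be reviewed as a serious adverse event". No pause is attached to this review.
- **Suspected causation:** the condition is "If there are any concerns that a leak has been caused by the BioGlue applied". The stated consequence is "then a serious adverse device effect has occurred, and the study paused while this is reviewed".
- **Run of leaks:** "If there are 5 consecutive anastomotic leaks in a row, this will trigger an internal review and an independent data monitoring committee formed and convened". No pause is stated.
- **Excess of serious adverse events:** "If there are more SAEs than expected, raised by the research team inputting data, this will be highlighted to the PI". There is no threshold and no pause; the PI may then consider early termination.

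The same section calls a 20% leak rate acceptable and notes that consecutive leaks can arise by chance. Section 7.1 says that "consecutive patients will be included up to a total of 30". Section 10.5 says that after surgery "there is no option for the removal of BioGlue".

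**The concern.** The two leak rules in section 14.5 lead to different actions. One leak with a suspected device cause stops the study for review. Five leaks in a row start a review but are not said to stop anything. The committee is also formed only after the rule has fired, which lengthens the interval before anyone independent can advise.

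A numeric rule is there to catch a raised leak rate that case-by-case attribution misses. Section 12.1 lists anastomotic leak as an expected complication whether or not BioGlue is used, so each leak in a run can reasonably be judged ordinary. The pause based on causation may then never be invoked. Because the glue cannot be removed, a patient treated during the review carries the full exposure whatever the committee concludes.

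**Working it through.** The protocol gives no operating characteristic for the five-in-a-row rule, so there is no stated figure to reproduce. The check has a textual part and a numerical part.

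**Is a pause stated anywhere else?** Section 10.5 covers individual withdrawal and surgery abandoned before the anastomosis. Section 12.2 covers reporting of related and unexpected serious adverse events to the ethics committee. Section 12.3 covers recording of adverse events. None of them pauses the study after a run of leaks. The 20% in section 14.5 is an acceptable rate, not a trigger.

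**Inputs**
- Patients: 30 (section 7.1).
- Leak rate p: 20% (section 14.5); 30% and 40% are assumptions.
- Accrual: 30 patients over 12 months (section 9: "Recruitment is estimated to be completed within 12 months"), which is 30/52 = 0.577 per week.
- Set-up time: not given; 2, 4 and 12 weeks are assumptions.

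**Step 1. Chance that the rule fires.** Treat patients as independent, in order of surgery, and track the current run length (0 to 4). A leak moves the run up by one with probability p, a non-leak resets it to 0, and reaching 5 fires the rule. Iterating over 30 patients gives the probability that the rule fires at each patient t, and hence the mean number still to be treated, 30 − t.

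| Leak rate | P(rule fires) | Mean patients remaining, given firing |
|---|---|---|
| 20% | 0.67% | 12.6 |
| 30% (assumed) | 4.4% | 12.8 |
| 40% (assumed) | 15.6% | 13.1 |

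A simulation of 400,000 trials agreed: 0.68% and 12.5 at 20%, 15.5% and 13.2 at 40%.

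**Step 2. Patients scheduled during set-up** = 0.577 × weeks: 1.15 (2 weeks), 2.31 (4 weeks), 6.92 (12 weeks).

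**Step 3. Mean further exposure given firing**, taking min(remaining, scheduled) averaged over the firing time:

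| Leak rate | 2 weeks | 4 weeks | 12 weeks |
|---|---|---|---|
| 20% | 1.10 | 2.16 | 5.88 |
| 40% | 1.11 | 2.17 | 5.96 |

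**Step 4. Averaged over all trials** (Step 3 × P(fires)), for 4 and 12 weeks:
- At 20%: 0.0067 × 2.16 = 0.01 and 0.0067 × 5.88 = 0.04 patients.
- At 40%: 0.1556 × 2.17 = 0.34 and 0.1556 × 5.96 = 0.93 patients.

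Section 9 puts the centre's volume at about 70 operations a year. If all were enrolled, the weekly rate in Step 2 would be 70/52 = 1.35 instead of 0.577.

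**The case against.** The text is silent rather than wrong. It never says that recruitment continues, and nothing prevents the PI or the internal review from holding cases. The existing pause is also broad. Every leak is reviewed as a serious adverse event, section 12.3 requires a causality assessment for each adverse event, any concern suffices for a pause, and abnormal adherence at re-operation is only an example. To fall through the gap, five leaks must be reviewed without any concern about the glue.

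The set-up times and the higher leak rates are assumptions, and the internal review could act before any committee exists. The figures also count exposure, not harm. At an assumed 40%, the excess over 20% averages 0.34 × 0.20 = 0.07 to 0.93 × 0.20 = 0.19 leaks per trial. The rule does not fire at all in 84% of trials at 40%, and an added pause does nothing for those.

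Most of this stands as a limit on size, but it does not close the gap. The existing pause turns on a judgement about a particular leak. The protocol itself classes leak as expected regardless of BioGlue and allows that consecutive leaks may be chance, so five reviews can each record no device concern. Given firing at 40%, the excess is about 2.2 × 0.20 = 0.4 to 6.0 × 0.20 = 1.2 leaks, which is not negligible in a study of 30.

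**Conclusion.** The concern holds. Section 14.5 states a pause for suspected causation and none for its only numeric leak trigger, and no other section supplies one. Further patients may therefore be treated during the review unless someone separately invokes the device-effect pause.

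The gap is narrow if the leak rate is 20%: the rule fires in about 0.7% of trials. It matters mainly if BioGlue raises leaks, when firing becomes more likely and some 2 to 6 further patients could be exposed before the committee reports. That range assumes 4 to 12 weeks of set-up, 30 patients a year and independent outcomes. A review acting within 2 weeks would reduce it to about one patient. The change is worth making, since it alters what the trial does at its main safety trigger and costs almost nothing.

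**What to change.** Extend the existing pause to this trigger with one sentence in section 14.5: *After 5 consecutive anastomotic leaks, enrolment and BioGlue application are paused until the internal review and the independent data monitoring committee have reported.* The committee review stays mandatory, as now.

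Sample size, endpoints and analysis do not change. The cost is a recruitment delay if the rule fires by chance, in about 0.7% of trials at a 20% leak rate.
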